Active cooling will be achieved by embedding a TEC assembly into a standard prosthetic socket and liner. The TEC assembly is comprised of a thermoelectric cooling unit (TEC), heat sink, fan and heat spreader and has previously been tested under New England IRB (NEIRB) protocol NEIRB # 120160413/HRPO Log A-17885.2. An experimental socket with the integrated heat spreader will be fabricated for each amputee subject. The amputee subjects will either visit their prosthetist's office

Figure 1. TEC Module embedded into standard prosthetic socket for active cooling condition.

or LTI's in-house prosthetist for measurements and the new socket will be fabricated. The subjects may return for alignment and adjustment on the new socket.

Testing will measure the temperature, humidity, socket suspension and moisture accumulation of the limb when active cooling, moisture/thermal management, and no cooling is applied in order to determine the effectiveness of the proposed technology.

Walking will be used to increase the temperature of the limb in order to measure the system's ability to cool it as well as to determine subject perception of heat and comfort with the experimental liner and active cooling system as compared to the control liners and sockets.

Research participants will have socket temperature and moisture data collected while walking on a treadmill in the different conditions throughout different site visits. The active cooling from the ICE module will be completed with the experimental liner as well as with the control liner. The order of conditions with the experimental and control liners and the active cooling on or off will be randomized for each subject.

5. Study Population

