The subject will then perform in-laboratory testing to determine the effectiveness of an experimental liner to keep the limb cooler and dryer as compared to the control prosthetic liner. The order of conditions (Experimental Liner versus Control Liner, with or without the active cooling ICE unit) will be randomized.

Similar to what was done in a prior protocol under a previous effort (NEIRB # 120160413/HRPO Log A-17885.2), an array of temperature sensors will be attached to the subject’s residual limb before donning the socket and/or liner to give a more complete picture of the overall temperature distribution across the residual limb. Baseline readings will be taken of the residual limb temperature, the body’s core temperature via an oral thermometer, and the ambient temperature.

In addition, we will measure the amount of perspiration produced during each condition. The limb will be dried with a towel, so pre- and post-activity weight of the liner and towel will be measured and the difference in weight is attributed to the sweat produced during that condition as described by Wernke et al. [7]. Testing may also be performed in a thermal chamber that regulates the temperature of the testing area, such as that used by Klute et al. [8], to ensure that the subject will perspire.

In addition, humidity sensors will be attached to the subject's residual limb before donning the socket and/or liner similar to work completed by Cutti et al. [9]. These will allow a more complete picture of the onset of moisture on the residual limb during activity.

In addition, marks will be made with a skin safe marker on the leg where the top of liner rests before the subject begins the testing activity (such as walking on a treadmill). Once the testing activity has ended, the same mark will be made on the leg where the top of the liner rests. The distance between these lines will show any slippage that occurred during the activity which may be due to a lack of suspension.

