The subject will be asked to do the following tasks, similar to Klute et al. [3]: (1) an initial seated rest for up to 60 minutes to obtain baseline in-socket temperature data; (2) an activity to increase their body temperature, such as walking on a treadmill [2, 3] for up to 30 minutes; (3) a seated rest for up to 60 minutes; and (4) the liner and perspiration will be collected off the limb (with a towel) and weighed for changes. The second condition will begin once baseline temperatures have been reached and the test procedure repeated in the other condition

Throughout the in-lab test sessions, photos and/or videos may be taken to document such things as the location of the sensors on the limb, the temperature gradients across the limb (with a thermal camera), etc. At the end of each condition, subjective feedback on the comfort and temperature regulation of each condition will be obtained via a questionnaire developed during this effort. The participants would fill out the questionnaire rating parameters such as perceived comfort, intra-socket temperature, potential loss of suspension, etc.

This visit will take up to 4 hours.

This visit can be repeated at the subject's volition, if more data is required or if re-testing is needed.

Visit 3: The same tasks as described in Visit 2 will be completed using the same data collection process. The order of conditions (Experimental Liner versus Control Liner, with or without the active cooling ICE unit) will be randomized. The subject will perform in-laboratory testing to determine the effectiveness the ICE unit to cool and reduce moisture generation of a residual limb with an experimental liner as compared to with a standard control prosthetic liner.

We expect to demonstrate that even if the socket doesn't reduce the temperature during walking, it can cool the socket immediately upon cessation of walking, unlike the standard socket that produces the sustained high temperatures observed by Klute, et al. [3] and Huff, et al. [2]. This benefit is expected to increase with the addition of the experimental thermally conductive liner.

This visit will take up to 4 hours.

This visit can be repeated at the subject's volition, if more data is required or if re-testing is needed.

Once all testing is completed, the research participant will complete a questionnaire to describe their opinions on the comfort, look, and functionality of the experimental liner and ICE unit.

8. Study Conduct

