The fourth measure we will be using is a subscale of the validated Prostheses Evaluation Questionnaire (PEQ) [3]. The PEQ consists of 82 items grouped into nine subscales, each addressing a different aspect of prosthesis wear (pain, satisfaction, comfort, etc.). The PEQ scales are not dependent on each other, so it is reasonable to use only those scales of interest. We will be using the Residual Limb Health section which rates qualities such as in-socket perspiration and skin breakdown of the residual limb. For each scale used, all of the individual questions that make up that scale must be included. The questions refer to the prior 4 weeks and are scored using a visual analog scale (100mm line). There is no total score. A guide gives coding instructions for all questions and groups the questions under different subscales. Each subscale score is computed by excluding any unanswered questions and averaging the answers within each subscale.

Visit #2 & Visit #3 – Part #1 & Part #2 – Individual Liner Questionnaire

The custom individual liner questionnaire was developed to rate the different aspects of the experimental and control liner. This questionnaire will be completed immediately after each activity to rate the liner that was used during that activity.

Visit #2 & Visit #3 – Part #3 – Liner Comparison Questionnaire

The custom liner comparison questionnaire was developed to measure the subject's preference for different criteria between the experimental and standard liner. This questionnaire will be completed at the end of Visit #2 and Visit #3 after the subject has completed both sets of activities.

References

- [1] A. Finlay and G. Khan, "Dermatology Life Quality Index (DLQI)-a simple practical measure for routine clinical use," *Clinical and Experimental Dermatology*, vol. 19, no. 3, pp. 210–216, 1994.
- [2] H. Meulenbelt, J. Geertzen, M. Jonkman, and P. Dijkstra, "Skin Problems of the Stump in Lower-limb Amputees: 2. Influence on Functioning in Daily Life," *Acta Dermato Venereologica*, vol. 91, no. 2, pp. 178–182, 2011.
- [3] D. A. Boone and K. L. Coleman, "Use of the Prosthesis Evaluation Questionnaire (PEQ)," *JPO Journal of Prosthetics and Orthotics*, vol. 18, no. Proceedings, 2006.

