This example shows that the person who answered these questions feels that having coffee in the morning is important to him. He also thinks the coffee he has had lately has not been very good.

If he hadn't drunk any coffee in the last four weeks, he would have put a check by that statement instead of putting a mark on the line between **TERRIBLE** and **EXCELLENT**.

As in this example, make a mark across the line rather than using an X or an O.

Please answer all the questions.

Support for development of the PEQ was provided by the U.S. Department of Veterans Affairs.

[figure not shown]
Visit #1 – Part 4 – Residual Limb Health Scale

These questions are about YOUR PROSTHESIS

[figure not shown]
Q. Over the past four weeks, rate how much you sweat inside your prosthesis (in the sock, liner, socket).

[figure not shown]
R. Over the past four weeks, rate how smelly your prosthesis was at its worst.

S. Over the past four weeks, rate how much of the time your residual limb was swollen to the point of changing the fit of your prosthesis.

T. Over the past four weeks, rate any rash(es) that you got on your residual limb.

OR check I had no rashes on my residual limb in the last month.

U. Over the past four weeks, rate any ingrown hairs (pimples) that were on your residual limb.

QR check: I had no ingrown hairs on my residual limb in the last month.

V. Over the past four weeks, rate any blisters or sores that you got on your residual limb.

QR check I had no blisters or sores on my residual limb in the last month

Visit #2 – Part 1 – Individual Questionnaire

Liner: Control / Experimental

ICE Unit: Off / ON

Fill in the circle that best describes the liner you just walked with:

On a scale from 1-5 please rate:					
1. your comfort while standing with this liner	 1	 2	 3	 4	 5 Excellent
2. your ability to stand with this liner	 1	 2	 3	 4	 5 Excellent
3. your comfort while walking with this liner	 1	 2	 3	 4	 5 Excellent
4. your ability to walk with this liner	 1	 2	 3	 4	 5 Excellent

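### Does randomizing liner and ICE on/off in one order clash with the end-of-visit form that compares the two liners?

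*Protocol*

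**What the plan says.** Section 4 sets the rule for the whole study: "The order of conditions with the experimental and control liners and the active cooling on or off will be randomized for each subject". Section 7 repeats it in the descriptions of both Visit 2 and Visit 3: "The order of conditions (Experimental Liner versus Control Liner, with or without the active cooling ICE unit) will be randomized". Crossing two liners with ICE on or off gives four conditions.

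Each test visit runs two of them. Section 7 puts it this way: "The second condition will begin once baseline temperatures have been reached and the test procedure repeated in the other condition". The stated aim of Visit 2 is to "determine the effectiveness of an experimental liner to keep the limb cooler and dryer as compared to the control prosthetic liner". The aim of Visit 3 concerns how well the ICE unit can cool and "reduce moisture generation of a residual limb with an experimental liner as compared to with a standard control prosthetic liner". Section 7 also lets either visit be repeated "if more data is required or if re-testing is needed".

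On the forms, Appendix A says of the liner comparison questionnaire: "This questionnaire will be completed at the end of Visit #2 and Visit #3 after the subject has completed both sets of activities". In Appendix B that questionnaire offers experimental, control or no preference on 11 criteria, under one ICE on/off field. The individual questionnaire is completed after each activity, has its own liner and ICE fields, and is headed: "Fill in the circle that best describes the liner you just walked with".

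Section 14 makes residual limb temperature the primary outcome and places satisfaction among the secondary measures. It compares experimental with control liner both with and without active cooling.

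**The concern.** Read alone, Section 4 and the repeated sentence in Section 7 allow any order of the four conditions. Nothing says that the two conditions of one visit share an ICE state, or even that they use different liners. The comparison form presumes both.

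Two kinds of order would break it. If a visit tests one liner twice, with ICE on and then off, the Visit 2 form asks for a preference between liners when only one has been tested. If a visit changes liner and ICE together, the answers on sweating and socket temperature mix the liner with the cooling, and the single ICE field has no correct entry. In the one-liner orders the liner contrast on temperature would also fall between visits, and so pick up day-to-day variation.

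**Working it through.** The protocol gives no figure to reproduce here. The check is a count of orders, a variance comparison and a side-by-side reading.

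**Count of orders.** Inputs: four conditions (Section 4) and two per test visit (Section 7, Appendix A). Assumptions: all orders equally likely, no repeat visits. There are 4! = 24 orders, with the first two conditions at Visit 2 and the last two at Visit 3. Given the first condition, each of the other three is equally likely to share its visit:

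| Pairing within each visit | Orders | Comparison form |
|---|---|---|
| Both liners, same ICE state | 8 | fits |
| One liner, ICE on and off | 8 | no liner comparison within the visit |
| Liner and ICE both change | 8 | liner mixed with cooling |

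So 16/24 = 2/3 do not fit. For 12 subjects (the target in Section 5, which does not say which group it covers), the expected number is 12 × 2/3 = 8, with a 95% binomial range of 5 to 11. Of these, 12 × 1/3 = 4 (1 to 7) would have one-liner orders. If ICE is held constant within a visit, the admissible orders number 2 × 2 × 2 = 8 and none misfits.

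**Effect on the temperature contrasts.** Let r be the ratio of day-to-day to within-day variance. The protocol does not give it, so r = 0.1, 0.5, 1 and 2 is an assumed range. In any order, exactly one of the three contrasts (liner, ICE, interaction) falls between visits, with variance factor 1 + 2r. The other two fall within visits, with factor 1. Factors are relative to no day-to-day variance.

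- Free draw, mixed model: each contrast is between visits in one third of orders, so its factor is 1/(2/3 + (1/3)/(1 + 2r)) = 1.06, 1.20, 1.29, 1.36, and never above 1.5.
- ICE constant within visit: the liner contrast and the interaction have factor 1. The ICE contrast has factor 1 + 2r = 1.2, 2, 3, 5.
- Both liners in every visit, ICE free (16 orders): the ICE-averaged liner contrast has factor 1. The ICE contrast has 1/(1/2 + (1/2)/(1 + 2r)) = 1.09, 1.33, 1.50, 1.67. In 8 of these 16 orders the preference answers still mix liner with cooling.

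**Side-by-side reading.** The Visit 2 aim is liner against liner, and the Visit 3 aim is liner against liner with the ICE unit. One-liner visits contradict both aims. A liner preference form closes each visit, which again requires both liners in it. Its single ICE field implies one ICE state. Section 14 compares liners at each ICE state, which is what such visits deliver. Only the general randomization sentence, taken in isolation, allows anything else.

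**The case for a change.** The strongest case for acting is that the restriction is written nowhere, and that the visit aims do not fully supply it. Read literally they tie ICE to Visit 3, which sits badly with randomizing ICE on/off and with the same sentence appearing under both visits. Three lists could be built: ICE tied to a visit, ICE randomized to visit, or a free draw. The forms are part of the protocol, so the mismatch lies within one document, and a sentence would be cheap.

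The gap in the wording is real, and so is the uncertainty over whether ICE state is randomized to visit. Neither makes the free draw a likely reading. Both of the other lists satisfy the comparison form, since each keeps one ICE state per visit with both liners. All testing takes place at one facility under one group of investigators, who also administer the forms.

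The obvious sentence is not free of cost either. Randomizing ICE to visit would put ICE on at Visit 2 and off at Visit 3 in half the sequences, against the stated aim of Visit 3. It also moves the ICE contrast between visits: at r = 1 its variance factor goes from 1.29 to 3. The looser rule keeps more precision for ICE but leaves half its orders mixing liner with cooling. That choice belongs to the sponsor and does not correct an error.

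A related point is that Section 14 lists the skin, limb-health and general quality-of-life questionnaires next to the satisfaction outcome. Section 7 and Appendix A already place them at Visit 1 and about the current liner. The custom questionnaires carry the comparison between conditions, so no result changes.

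**Conclusion.** No change follows. The protocol leaves a restriction unwritten, but its visit aims, forms and planned comparisons together supply it, and staff preparing the randomization list would be expected to fill the gap sensibly. Under that reading the number of misfitting orders is zero.

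The figure of 16 in 24 orders, or 8 of 12 subjects, rests on an equal draw over all orders, two conditions per visit and no repeat visits. The protocol does not state that draw. Even then the harm is confined to a custom, non-primary preference form. The temperature contrasts remain within subject, with a liner variance factor of 1.06 to 1.36 over the assumed r and at most 1.5. The individual ratings of comfort, warmth, sweating and suspension stay correctly labelled by liner and ICE state. Fixing one ICE state per visit would bring the liner factor to 1 but raise the ICE factor to between 1.2 and 5 over the same range, which is a trade-off and not a clear gain.

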Moisture Management Liner Effectiveness Study

Investigators	[name] Liberating Technologies, Inc. [name] [contact]
	[name] Vivonics, Inc. [name]
Sponsor	U.S. ARMY MEDICAL RESEARCH ACQUISITION ACTIVITY (USAMRAA)
Sponsor Protocol #	E00572.1a
Solutions IRB #	2020/01/01

1. Background and Introduction

The comfort and fit of the residual limb within a prosthetic socket are of primary concern for many amputees. The residual limb is typically covered by non-breathable and non-thermally conductive materials that can create a warm and ultimately moist environment. These layers consist of a prosthetic liner that rolls onto the limb and traps heat and occasional extra prosthetic socks. Studies found increases in socket temperature after the prosthesis was donned (0.8°C) [1] and after 30 minutes of walking (2.5°C) [2]. Temperatures were found to remain elevated long after activity cessation and even a rest period of double the duration of the preceding activity period is insufficient to return the limb to its initial temperature [3]. Peery, et al. [1] suggested that a modest temperature increase of only 2°C may be responsible for reports of thermal discomfort by amputees. Therefore, a small amount of activity can cause the socket temperature to elevate and remain at an uncomfortable level for an extended period of time, which can lead to decreased wear times. In summary, an uncomfortable socket/residual limb interface decreases prosthesis use among amputees who want to remain active in their lives.

To address this, Vivonics, Inc. and Liberating Technologies, Inc. (LTI) have developed a silicone liner approach to wick sweat from the skin and out of the socket through specially designed microchannels and to passively conduct heat from the skin using thermally conductive elastomers. This liner has been developed to work alongside a thermo-electric cooling (TEC)-based module called the Intrasocket Cooling Element (ICE) developed in a parallel project by Vivonics and LTI. The ICE device can be embedded into the prosthesis in order to cool the residual limb. A technology that can provide thermal control while retaining adequate suspension, weight, and other prosthetic characteristics would benefit many prosthesis wearers.

2. Study Rationale

This study will focus on investigating the efficacy of this novel moisture and thermal management (experimental) liner.

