The rationale for this study is to determine how well the new technology can regulate the residual limb temperature, reduce the moisture generation, and remove excess moisture in a controlled laboratory environment.

3. Objectives

The primary objective of this study is to measure the effects experimental techniques of moisture and thermal management has on moisture and temperature in the socket. Moisture and thermal management of the residual limb inside the prosthetic socket could result in greater comfort while wearing the prosthesis, and ultimately could result in greater function and better quality of life (QoL).

4. Study Design

A repeated measures study will be conducted to analyze the temperature and moisture generation of the residual limb with and without the experimental liner and active cooling system within a standard prosthetic socket.

Both able-bodied research subjects, and lower limb amputee research subjects who use transfemoral or transtibial prostheses will be recruited for testing. Liners for able-bodies subjects will have the distal end removed to allow for donning. All subjects will visit Liberating Technologies, Inc. to be consented and to complete study testing.

Test conditions include:

- **Control condition.** This would be a non-modified control liner (such as commercially off the shelf (COTS) liners or ones made without any additives) for able-bodied subjects and, for amputees, a check socket (with or without an unmodified control liner, depending on whether the amputee typically wears a liner or not).
- **Experimental liner condition.** This would be a prototype liner designed to reduce and/or remove moisture and heat that builds up on the limb.
- **Active cooling condition.** This would integrate the TEC module (see Figure 1) into the socket for amputees (with the experimental liner or with a control liner), or the TEC module with the experimental or control liner for able-bodied subjects.

Passive cooling and moisture management will be achieved from an experimental liner made of standard silicone used in COTS liner with bio-compatible thermally conductive additives. A standard check socket will be fabricated for each amputee subject if necessary to fit the experimental liner. Additional modifications, such as channels in a liner and socket, may be used to remove moisture such as ones developed under New England IRB (NEIRB) protocol NEIRB # 14-232/HRPO Log A-17885.

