Subjects will be consented and screened for eligibility criteria. If they decide to participate, an experimental liner will be made that fits the size and shape of their limb and an experimental socket to fit the experimental liner will be fabricated using standard prosthetic techniques.

Subjects may withdraw at any time by simply telling the investigators they wish to stop their participation.

If a subject withdraws from the study, the data that were collected from them can still be used, and the withdrawn subjects may be replaced with a new subject. Deviations from the protocol that increase risks for subjects will be reported to Solutions IRB and HRPO for approval prior to being implemented.

The consent process and all testing will be completed at the Liberating Technologies, Inc. research facility located in Holliston, MA. Approved study staff from Vivonics, Inc. may also be present during testing visits to provide technical support or monitor testing activities. During these visits approved study staff from Vivonics, Inc. may be in contact with the subjects.

Subjects will be compensated \$40 per hour for the 3 visits for the in-lab testing and prosthetist visits for an estimated total of \$400 (10 hours) per subject. Travel will also be reimbursed per mile at the current IRS federal rate.

9. Study Treatment

This is not a treatment study. The purpose of the study is to evaluate the effectiveness of a moisture removal and thermally conductive liner.

10. Evaluation of Adverse Events

Based on past testing and data collection, no adverse events are expected. Adverse events could include: discomfort or dermatological reaction to experimental liner materials or sensors in the socket, tripping while walking on the treadmill, overheating or overcooling due to controller, sensor, or battery malfunction of the ICE unit. These risks have been mitigated by using biocompatible materials and/or hypoallergenic tape with the sensors, using a spotter during walking tasks for in-lab testing, and standard thermal and electrical management techniques including thermal battery management, voltage/current limiting, and monitoring temperature during testing.

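### The liner-and-towel weight is read as sweat produced, but it captures only moisture still present at weighing, so a difference in sweat expelled can be reported as a difference in sweating

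*Protocol*

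**What the plan says.** Section 7, Visit 2, sets out the purpose: "we will measure the amount of perspiration produced during each condition". Only the liner and the towel are weighed, and "the difference in weight is attributed to the sweat produced during that condition", with a published liner study cited for the method. In the task list of the same visit, weighing is the fourth step, after an initial rest, the walk and a second seated rest: "the liner and perspiration will be collected off the limb (with a towel) and weighed for changes".

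Other sections describe what the experimental product is for. Section 1 says the approach is to "wick sweat from the skin and out of the socket through specially designed microchannels". Section 9 gives the study's purpose as to "evaluate the effectiveness of a moisture removal and thermally conductive liner". Section 4 adds that modifications "such as channels in a liner and socket, may be used to remove moisture". Section 2 lists two effects side by side, to "reduce the moisture generation, and remove excess moisture in a controlled laboratory environment".

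Section 14 names limb temperature as the primary outcome and puts moisture generation among the secondary measures. The Visit 3 text in Section 7 also speaks of moisture generation when it compares the ICE unit between the two liners. Sections 4 and 13 use moisture accumulation instead.

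**The concern.** Section 2 treats less sweating and better removal of sweat as separate effects. A weight taken from the liner and towel cannot separate them when two different liners are compared. Suppose the experimental liner carries sweat away and leaves sweating unchanged. Less moisture is then found at weighing, and under the Section 7 rule this is reported as less sweat produced. If instead the control loses more, a real reduction could be hidden.

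The weighing itself is sound. Moisture retained at the end of a condition is a fair answer to the Visit 2 question of whether the limb stays dryer. The fault is in calling that quantity production.

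**Working it through.** The protocol gives no figure to reproduce here, so the check is a mass balance.

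**What is and is not captured (Section 7)**
- Weighed: the liner and the towel used to dry the limb.
- Not weighed: the socket, the gel sock where one is worn, and anything that dripped, was wicked out or evaporated. The humidity sensors are there to show the onset of moisture and give no mass.
- Time for sweat to leave, at the stated maxima: 30 + 60 = 90 minutes from the start of walking, or 60 + 30 + 60 = 150 minutes with the initial rest.

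**Formula**

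Let S be sweat produced and f the fraction gone from liner and limb before weighing. The measured weight is M = S × (1 − f). Between liners,

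M_exp / M_ctl = (S_exp / S_ctl) × (1 − f_exp) / (1 − f_ctl).

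This equals the production ratio only if f_exp = f_ctl.

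**Illustration between liners** (every f and every true ratio is an assumption)

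| True ratio | f_exp | f_ctl | Measured ratio | Reads as |
|---|---|---|---|---|
| 1.00 | equal | equal | 1.000 | no change |
| 1.00 | 30% | 0% | 0.70/1.00 = 0.700 | 30% reduction |
| 1.00 | 30% | 10% | 0.70/0.90 = 0.778 | 22.2% reduction |
| 1.00 | 10% | 20% | 0.90/0.80 = 1.125 | 12.5% increase |
| 1.00 | 0% | 30% | 1.00/0.70 = 1.429 | 42.9% increase |
| 0.90 | 30% | 0% | 0.90 × 0.70 = 0.630 | 37% reduction |
| 0.90 | 0% | 10% | 0.90/0.90 = 1.000 | no change |
| 1.20 | 25% | 0% | 1.20 × 0.75 = 0.900 | 10% reduction |

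The last row shows that the sign can reverse. The range depends on the fractions assumed: a loss of 75% against 0% would read as a 75% reduction.

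**ICE on versus off within one liner, equal production**
- f of 30% in both states: 0.70/0.70 = 1.000, no bias.
- f_on 20%, f_off 30%: 0.80/0.70 = 1.143, a false 14.3% increase.
- f_on 30%, f_off 20%: 0.70/0.80 = 0.875, a false 12.5% reduction.

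This contrast is less exposed, but only if the fraction is the same with ICE on and off, which the protocol does not state.

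**ICE effect compared between liners (Visit 3), in grams**

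Take an assumed true effect of 2.0 g in both liners, with f unchanged by ICE. It reads 2.0 × (1 − 0.30) = 1.4 g in the experimental liner at f = 30%, and 2.0 × (1 − 0) = 2.0 g in the control at f = 0%. Here the error runs against the experimental liner.

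**The case against.** **Differential loss is not shown.** Section 4 makes channels optional, and the product text in Section 13 describes hydrophobic silicone with thermal additives, so the version tested may expel little. Control liners can lose sweat too: those for able-bodied subjects "will have the distal end removed to allow for donning". This stands, and it is why neither size nor direction can be claimed. It does not rescue the attribution, which Section 7 makes whichever version is tested and without requiring equal losses.

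**The method is cited.** The source is not at hand, so any handling of expelled sweat in it cannot be checked. A citation does not change what is weighed here.

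**The times are ceilings.** Two conditions of 150 minutes need 300 minutes, but a visit is limited to 4 hours (240 minutes). Both conditions in one visit therefore cannot reach the maximum. Elapsed time also does not show unequal loss between liners. Both points are correct; the formula does not depend on them.

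**The consequence is limited.** Moisture is secondary in Section 14, and humidity sensors and a sweat rating after each condition also inform the comparison. That limits the harm, but neither gives a mass of sweat produced. The Section 3 objective also names moisture alongside temperature, so the measure is not peripheral.

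**Moisture generation in Section 14 may not mean this weight.** That link is an inference. It rests on weighing being the only objective procedure in the protocol that quantifies sweat.

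**Conclusion.** The concern holds. The weight change is production less whatever left the liner and limb before weighing, so the attribution in Section 7 is wrong as written. Confidence is high on that point only.

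Whether a bias arises, how large it is and which way it runs all depend on expelled fractions that the protocol does not give. If the experimental liner expels more, as its description intends, the error in the liner contrast flatters it. The percentages shown illustrate assumed fractions and do not estimate this study's bias. The matter should be corrected before results are interpreted, but it does not touch the temperature outcome.

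**What to change.** 1. In Section 7, Visit 2, replace both references to perspiration or sweat produced with *moisture retained in the liner and on the limb*.
2. In the Visit 3 text of Section 7 and in Section 14, replace moisture generation with *retained moisture*, or with *moisture accumulation*, the term already used in Sections 4 and 13.
3. State that no conclusion on sweat production is drawn from this weight in the experimental-versus-control liner contrast, including the Visit 3 comparison of ICE between liners. State also that any such conclusion from ICE on versus off within one liner assumes the same expelled fraction in both states.

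Section 2 can stand, because the within-liner ICE contrast can still address moisture generation under that assumption.

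The cost is wording in Sections 7 and 14, with no change to data collection. The study gives up any claim of reduced sweat production from this measure in the liner contrast. Keeping that claim would require the expelled sweat to be captured and weighed as well, including what is held in the socket and sock, which is a change of procedure.
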